
Inclusion Criteria:
	
To be eligible for participation in the study, patients must meet all of the following inclusion criteria:
 
During Prescreening:
 
 1. Be between the ages of ≥ 18 and ≤ 65 years

	
 2. Have an established, pathologically confirmed diagnoses of AML by World Health Organization (WHO) criteria excluding acute promyelocytic leukemia (APL-M3) with a bone marrow of >5% blasts based on histology or flow cytometry 3. Be in first relapse (within 24 months of CR) or have failed induction therapy* (no CR or CRi after treatment with an intensive regimen [eg, anthracycline/cytarabine ± etoposide, gemtuzumab ozogamicin, or cladribine]) *Induction therapy may involve 1 or 2 cycles of the same regimen. Efficacy assessment of induction therapy must be >21 days from the start of the previous induction cycle. 4. Demonstrate MCL-1 dependence of ≥30% by mitochondrial profiling in bone marrow 
During Screening:
 
 5. Have an Eastern Cooperative Oncology Group (ECOG) performance status (PS) ≤2 6. Have a serum creatinine level ≤1.8 mg/dL 7. Have an alanine aminotransferase (ALT)/aspartate aminotransferase (AST) level ≤5 times upper limit of normal (ULN) 8. Have a total bilirubin level ≤2.0 mg/dL (unless secondary to Gilbert syndrome, hemolysis, or leukemia) 9. Have a left ventricular ejection fraction (LVEF) >45% by echocardiogram (ECHO) or multigated acquisition (MUGA) scan 10. Be nonfertile or agree to use an adequate method of contraception. Sexually active patients and their partners must use an effective method of contraception associated with a low failure rate during and for at least 6 months after completion of study therapy (see Section 4.7.3). 11. Be able to comply with the requirements of the entire study. 12. Provide written informed consent prior to any study related procedure. (In the event that the patient is re-screened for study participation or a protocol amendment alters the care of an ongoing patient, a new informed consent form must be signed.)

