11.4.3 Pharmacodynamic Endpoint Analyses

Summary of baseline biomarker values will include within- and between-treatment-arm descriptive statistics. A logistic regression model will be fit to examine the relationship between baseline MCL-1 dependence and the independent binary variable achievement of CR during the study. The full model will include effects for baseline MCL-1 dependence, treatment arm, and the two-way interaction between baseline MCL-1 dependence and treatment arm. In addition, area under the curve (AUC) and 95% CI will be calculated (by treatment

arm) for the trapezoidal receiver operating characteristic curve. This value will quantify the ability of MCL-1 dependence to predict CR.

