List of Appendices

Appendix 1. Criteria for Grading Severity of Clinical Tumor Lysis Syndrome.....	33
Appendix 2. Sample Summary Table Templates	34

1. Synopsis

Protocol Title:

A Phase 2, Randomized, Biomarker-Driven, Clinical Study in Patients with Relapsed or Refractory Acute Myeloid Leukemia (AML) with an Exploratory Arm in Patients with Newly Diagnosed High-Risk AML and Exploratory Arms with Varying Levels of MCL-1 Dependence

Study Design:

There is a primary study component and four exploratory study arms

- Primary Study: single-arm, Simon two-stage lead in to confirm efficacy assumptions followed by a randomized, two-arm parallel design
- Exploratory Study Arms: single-arm observational

Study Populations:

- Primary Study: Relapsed and refractory AML patients with MCL-1 dependence $\geq 40\%$
- Exploratory Study Arms:
 - Patients with newly diagnosed, high-risk AML and MCL-1 dependence $\geq 40\%$
 - Relapsed and refractory AML patients with MCL-1 dependence between 0% and $< 15\%$
 - Relapsed and refractory AML patients with MCL-1 dependence between 15% and $< 30\%$
 - Relapsed and refractory AML patients with MCL-1 dependence between 30% and $< 40\%$

Treatment Arms:

- ACM (alvocidib, Ara-C [cytarabine] and mitoxantrone)
- CM (Ara-C [cytarabine] and mitoxantrone)

Biomarker:

- MCL-1 dependence measured by mitochondrial sensitivity to NOXA BH3 peptides (hereafter referred to as MCL-1 dependence)

Sample Size:

- Primary Study, Stage 1: up to 23 patients
- Primary Study, Stage 2: 106 patients (53 patients per treatment arm)
- Exploratory Study Arms: 20 patients in each of four exploratory patient populations

Randomization:

- Primary Study, Stage 1: Not randomized, all patients receive ACM

- Primary Study, Stage 2: Randomized 1:1 to ACM or CM stratified by response to frontline AML therapy
- Exploratory Study Arms: Not randomized, all patients receive ACM

Analysis Populations:

Intent-to-treat (primary for efficacy), safety, response-available, per-protocol, crossover

Response Assessments:

Central review performed by a panel of independent, expert hematologists according to an approved charter under change control (primary response assessment); local review of bone marrow and blood test results by the investigator at the study center where patient is enrolled (secondary assessment); “sponsor review” by employees and/or agents of Tolero Pharmaceuticals

Missing Values:

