5.1. Primary Study

5.1.1. Stage 1

The sample size of 23 eligible patients for stage 1 was selected because it allows estimation of the CR rate by means of a 90% confidence interval with maximum width of $\pm 17\%$. Although this study does not follow a Simon 2-stage design, 23 patients is consistent with the sample size for stage 1 of the Simon 2-stage minimax design with 80% power for testing the null hypothesis that the CR rate is 50% against a one-sided alternative at the 5% level of significance when the actual CR rate is 70%. In the Simon

2-stage design described, the study would continue to stage 2 only if 13 patients achieve remission out of a maximum of 23 eligible patients. Therefore, this was selected as the requirement to proceed to stage 2 of this study.

5.1.2. Stage 2

The total planned sample size of 106 patients (53 per treatment arm) in stage 2 of the primary study provides 90% power to reject the null hypothesis of equal cycle-1 CR rates across treatment arms under the following conditions:

- Cycle-1 CR rates of 70% and 40% for patients receiving ACM and CM, respectively
- One-sided 2.5% significance level
- A single interim analysis of cycle-1 CR rates using O’Brien-Fleming boundaries¹ (see section 7.5.1) after responder status has been defined for 56 patients (28 per treatment arm)
- Randomization based on a 1:1 patient allocation ratio (ACM to CM)

Table 2 lists the programming statements used in SAS (version 9.4) to compute the sample size. Relevant SAS output is shown in Table 3 and Table 4.

Table 2. SAS Programming Statements for Sample Size Calculation

```
proc seqdesign boundaryscale=pvalue;
    design alpha=0.025 alt=upper beta=0.1 info=cum(56 106) method=obf nstages=2;
    samplesize model=twosamplefreq(nullprop=0.40 prop=0.70 test=prop weight=1);
run;
```

Table 3. SAS PROC SEQDESIGN Output: Boundary Information

Stage				Alternative	Boundary Values
	Information Level			Reference	Upper
	Proportion	Actual	N	Upper	Alpha
1	0.5283	62.2073	55.98657	2.36615	0.00321
2	1.0000	117.7495	105.9746	3.25537	0.02378

Table 4. SAS PROC SEQDESIGN Output: Sample Sizes

Stage	Fractional N				Ceiling N			
	N	N(Grp 1)	N(Grp 2)	Information	N	N(Grp 1)	N(Grp 2)	Information
1	55.99	27.99	27.99	62.2073	56	28	28	62.2222

Table 4. SAS PROC SEQDESIGN Output: Sample Sizes

Stage	Fractional N				Ceiling N			
	N	N(Grp 1)	N(Grp 2)	Information	N	N(Grp 1)	N(Grp 2)	Information
2	105.97	52.99	52.99	117.7	106	53	53	117.8

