7.5.2. Type-1 Error Rate Control for Multiple Comparisons

Without taking appropriate measures, testing multiple efficacy parameters inflates the overall significance level since the probability of making a type-1 error in at least one from a set of hypothesis tests is greater than the probability of making a type-1 error in any single test. The hierarchical closed test procedure^{3,4} will be used to maintain the overall 2.5% significance level.

The order of efficacy endpoints for the hierarchical closed test procedure is:

1. Cycle-1 CR rate
2. Progression-Free Survival
3. Stem Cell Transplant Rate
4. Cycle-1 Combined CR Rate
5. Cycle-1 Combined Remission Rate
6. Overall Survival
7. Combined Remission Duration
8. Combined CR Duration
9. CR Duration

The final analysis will be conducted at a one-sided 2.378% significance level using the statistical procedures described below. Cycle-1 CR rate, the primary efficacy endpoint, will be declared statistically significant if its test p-value ≤ 0.02378 . A secondary efficacy endpoint will be declared statistically significant only if its test p-value ≤ 0.02378 and all efficacy endpoints preceding it in the hierarchy are statistically significant. In other words, declaration of statistical significance for efficacy endpoints will advance in order down the hierarchy only until a p-value > 0.02378 is found.

In addition, although primary and supportive analytical methods are specified for each endpoint in the hierarchy, only the p-value from the primary analysis will be used for deciding statistical significance. Supportive (sensitivity) analyses are to demonstrate the robustness of primary results to slight modifications to how endpoints are defined and/or analyzed.

Declarations of statistical significance will not be advanced for endpoints not included in the hierarchy of the closed test procedure (e.g., ECOG performance status).

It is worthwhile noting...

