Hypothesis testing will be based on the stratified Cochran-Mantel-Haenszel (CMH) general association test statistic^{6,7} (see Table 5). Stratification levels will be the same as those used for the randomization scheme (see section 6). Although the alternative hypothesis for the CMH general association test statistic is that cycle-1 CR is correlated with treatment arm in at least one stratum, the statistic has low power for detecting an association in which the patterns of association for some of the strata are in the opposite direction of the patterns displayed by other strata.⁸ Therefore, a statistically significant CMH general association statistic will validate the positive contribution of alvocidib (added to CM) to induce CR (over CM alone).

Within–treatment-arm statistics will include the number and percentage of patients rated as not achieving CR due to not providing a bone marrow biopsy/aspirate, proportion of patients who achieve a cycle-1 CR and exact 95% CI estimated without stratification. Between–treatment-arm statistics will include the Mantel-Haenszel odds ratio and 95% CI estimated with stratification.

A standard logistic regression (LR) model will be estimated relating the probability of a cycle-1 CR as a function of baseline MCL-1 dependence, treatment arm, and the two-way interaction between baseline MCL-1 dependence and treatment arm. If the p-value for the Wald chi-square statistic for two-way interaction is >0.10, then the Wald chi-square statistic for treatment arm will be interpreted as testing the equality of cycle-1 CR rates controlling for the effect of baseline MCL-1 dependence. Results will be presented graphically as follows. Patients will be divided into groups according to which range of values their baseline MCL-1 dependence falls:

$$(0\%-\leq d_1), (d_1-\leq d_2), (d_2-\leq d_3), \dots, (d_8-\leq d_9), (d_9-100\%)$$

where d_1, \dots, d_9 are deciles for baseline MCL-1 dependence regardless of treatment arm. Empirical within–treatment-arm cycle-1 CR rates will be calculated for patients within each range and plotted alongside cycle-1 CR probabilities estimated from the LR model.

Table 5. Statistical Analyses of Cycle-1 CR Rates

Analysis Population	Analytical Method	Response Assessment	Role of Analysis
Intent-to-Treat	Stratified CMH	Central	Primary
Intent-to-Treat	Stratified CMH	Local and Sponsor	Supportive

Table 5. Statistical Analyses of Cycle-1 CR Rates

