Analysis Population	Analytical Method	Response Assessment	Role of Analysis
Intent-to-Treat	Logistic regression	Central	Supportive
Intent-to-Treat	Logistic regression	Local and Sponsor	Supportive
Per-Protocol	Stratified CMH	Central	Supportive
Per-Protocol	Stratified CMH	Local and Sponsor	Supportive
Per-Protocol	Logistic regression	Central	Supportive
Per-Protocol	Logistic regression	Local and Sponsor	Supportive
Response-Available	Logistic regression	Central	Supportive
Response-Available	Logistic regression	Local and Sponsor	Supportive
Subgroups based on patient characteristics	Logistic regression	Central, Local and Sponsor	Exploratory

If the test for between-treatment-arm homogeneity of any baseline characteristic gives two-sided p-value <0.10, then the effect that baseline characteristic has on cycle-1 CR rate will be quantified using LR. Two LR models will be fit. One model will include the baseline characteristic in question as the only independent variable, and the second model will include the baseline characteristic and the stratification factors used for randomization.

Other remission rates (e.g., cycle-1 combined CR rate and cycle-1 combined remission rate) will be summarized similar to cycle-1 CR rate.

Correlation between central and local review will be assessed descriptively in 2-way frequency tables, both as a bivariate response (CR yes or no) and on the full scale (CR, CRi, CRp, PR, resistance/relapse). The simple kappa coefficient^{8,9} will be calculated as a measure of agreement between the central and local reviews. Since the two response variables are two independent ratings of the same tissue sample, the kappa coefficient equals 1 when there is complete agreement of the raters. When the observed agreement exceeds chance agreement, kappa is positive, with its magnitude reflecting the strength of agreement. Although this is unusual in practice, kappa is negative when the observed agreement is less than chance agreement.⁸

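### SAP 7.9.1: the supportive logistic test of treatment is read from a model that keeps an uncentred MCL-1-by-treatment interaction, giving about 2-9% power where a refit without it gives 86-88%

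*SAP*

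**What the plan says.** SAP 7.9.1 specifies a standard logistic model for cycle-1 CR with three terms: baseline MCL-1 dependence, treatment arm and their two-way interaction. When the Wald p-value for the interaction is above 0.10, "then the Wald chi-square statistic for treatment arm will be interpreted as testing the equality of cycle-1 CR rates", controlling for MCL-1. No second model is named and no centring is mentioned. SAP section 7 applies SAS 9.4 default estimation methods unless stated otherwise, and restricts inference on the efficacy objectives to Stage 2.

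Protocol 11.4.3 has the same three terms: "The full model will include effects for baseline MCL-1 dependence, treatment arm, and the two-way interaction". It names no reduced model.

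For the further remission endpoints, SAP 7.9.1 adds: "Other remission rates (e.g., cycle-1 combined CR rate and cycle-1 combined remission rate) will be summarized similar to cycle-1 CR rate".

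The purpose of such analyses is given in SAP 7.5.2: "Supportive (sensitivity) analyses are to demonstrate the robustness of primary results".

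On the range of MCL-1, the SAP synopsis gives "Primary Study: Relapsed and refractory AML patients with MCL-1 dependence" of at least 40%, and the protocol's inclusion criteria say "Demonstrate MCL-1 dependence of ≥30% by mitochondrial profiling in bone marrow".

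**The concern.** In a model with treatment T, covariate X and T×X, the coefficient of T is the treatment log odds ratio at X = 0. A non-significant interaction does not change this, because the term stays in the model. Here X = 0 means MCL-1 dependence of 0%, which is 30 or 40 points below the lowest value that any Stage 2 patient can have. The Wald test is therefore an extrapolation outside the data, and not a test of equal CR rates over the enrolled range. Switching between reference and effect coding of treatment does not help, since both give a test at MCL-1 = 0%.

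The issue is lost power. With no true interaction the coefficient still targets the common odds ratio, but very imprecisely. At stake is the credibility of the supportive analyses. Of the nine supportive rows in SAP Table 5, six are logistic regressions, and they are the ones that adjust for the biomarker on which the trial is built. If the trial succeeds, they would usually be non-significant, and that artefact would look like lack of robustness.

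**Working it through.** **Inputs.**
- SAP 5.1.2: 53 per arm, "Cycle-1 CR rates of 70% and 40% for patients receiving ACM and CM, respectively", "One-sided 2.5% significance level". SAP 7.5.1 and 7.5.2: final one-sided level 0.02378, critical value 1.981.
- Protocol 11.2.2: 28 per arm, CR 70% vs 30%, one-sided 2.5%, critical value 1.960.
- Interaction threshold: p > 0.10 (SAP 7.9.1).
- Assumed, because the documents give no Stage 2 MCL-1 distribution: uniform from the cutoff to 70%; uniform from the cutoff to 100%; normal (mean 50, SD 15) truncated to cutoff-100%. CR is taken as independent of MCL-1.

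**1. The plan's own figures reproduce.** Fixed-design n per arm = (1.960 + 1.282)² × [p₁(1−p₁) + p₂(1−p₂)] / (p₁−p₂)².
- Protocol: 10.51 × 0.42 / 0.16 = 27.6, so 28.
- SAP: 10.51 × 0.45 / 0.09 = 52.5. Adding the O'Brien-Fleming interim at 56/106 gives a total of 105.97, with boundaries 0.00321 and 0.02378, as the SAP states.

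The documents state no power for the logistic test.

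**2. Why the standard error grows.** If CR does not depend on MCL-1 (mean m, SD s in each arm), then approximately
- SE of treatment, interaction removed: √[1/(n p₁(1−p₁)) + 1/(n p₂(1−p₂))]
- SE of treatment at MCL-1 = 0, interaction kept: the same × √[1 + (m/s)²]

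| MCL-1 (uniform) | m | s | √[1+(m/s)²] | Simulated SE ratio |
|---|---|---|---|---|
| 30-70% | 50 | 11.55 | 4.44 | 4.6 |
| 30-100% | 65 | 20.21 | 3.37 | 3.5 |
| 40-70% | 55 | 8.66 | 6.43 | 6.6 |
| 40-100% | 70 | 17.32 | 4.16 | 4.3 |

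**3. Rough power over all trials.**
- Protocol design, MCL-1 30-100%: log odds ratio = 2 ln(0.7/0.3) = 1.695. SE without the interaction = √(2/5.88) = 0.583; as written, 0.583 × 3.37 = 1.96. Power as written = P(Z > 1.960 − 1.695/1.96) = P(Z > 1.10) = 14%. Without the interaction: P(Z > 1.960 − 2.91) = 83%.
- SAP design, MCL-1 40-100%: log odds ratio = ln(0.7/0.3) − ln(0.4/0.6) = 1.253. SE = √(1/11.13 + 1/12.72) = 0.410; as written, 0.410 × 4.16 = 1.71. Power as written = P(Z > 1.981 − 0.73) = 11%. Without the interaction: P(Z > 1.981 − 3.05) = 86%.

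**4. Why the interaction threshold makes it worse.** The treatment coefficient at 0% and the interaction coefficient have correlation of about −m/√(m²+s²), which is −0.955 for 30-100%. Trials with a large positive treatment coefficient therefore tend to have a large negative interaction. The p > 0.10 rule removes many of these.

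**5. Simulation.** There were 4,000 trials per scenario, with maximum-likelihood fits and no true interaction. Power is given for trials with interaction p > 0.10 (89-90% of trials). The three values follow the order of the assumed distributions above.

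| Design | As written | Refit without interaction | SE ratio |
|---|---|---|---|
| 28/arm, 70% vs 30%, MCL-1 ≥30% | 3%, 7%, 4% | 86% | 4.6, 3.5, 4.5 |
| 53/arm, 70% vs 40%, MCL-1 ≥40% | 2%, 6%, 3% | 88% | 6.6, 4.3, 5.5 |
| 53/arm, 70% vs 40%, MCL-1 ≥30% (two uniform cases only) | 6%, 9% | 87-88% | |

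Over all trials, without conditioning on the interaction, power is 6-13% as written and 86-88% refitted. Keeping the interaction but centring MCL-1 also gives 86-88%.

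**6. Sensitivity.** A separate simulation with 6,000 trials per scenario and other spreads agreed.
- Even MCL-1 spread over 0-100%, which entry rules out, gives only 25-31% as written.
- If the benefit grows with MCL-1 (interaction log odds ratio 0.2-0.4 per 10 points, MCL-1 from 30% or 40% upward, SAP design), power as written is 0.3-2.5% and the refit keeps 84-88%. The coefficient at 0% can then even change sign: for MCL-1 40-100%, 1.25 − 7 × 0.4 = −1.55.

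**The case against.** The algebra is not in dispute. The case against concerns consequence and reading.

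- *It decides nothing.* Under SAP 7.5.2 only the primary p-value determines significance, and three supportive CMH rows are unaffected. This stands, and it limits the importance of the point.
- *The results are mainly graphical.* SAP 7.9.1 plots fitted CR probabilities by MCL-1 decile group. These do not depend on centring, and neither the CR-rate table template nor SAP Table 9 reserves a place for the Wald statistic. That is true, but the SAP says the statistic will be interpreted as a test of equal rates, and the plot does not repair that test.
- *The SAP does not actually say uncentred or unrefitted.* Its phrase about controlling for MCL-1, and the protocol's reference to a full model, would fit an intended main-effects model. This is possible, but where the SAP intends two models it says so, as for the baseline-imbalance logistic models (7.9.1) and the Cox models (7.9.2). A programmer following the text would fit one.
- *Some figures are for a superseded design.* The SAP cites Amendment 7, whereas the protocol has 28 per arm and MCL-1 ≥30%. Fair: the 28-per-arm row is the one for the current protocol, and it shows the same loss.
- *Carry-over to the other remission rates is less explicit.* The SAP says only that they are summarised similarly. This stands as a caution.

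**Conclusion.** The concern holds. As written, the rule tests the treatment odds ratio at MCL-1 = 0% and has 3-7% power under the protocol design and 2-9% under the SAP design, given interaction p > 0.10. The same data analysed without the interaction give 86-88%.

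The mechanism is certain. The exact percentages rest on assumed MCL-1 distributions and, for the main figures, on no true interaction. No spread compatible with the entry criteria that was tried brings the test near the refit.

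Not affected are the primary CMH decision and its type I error, the supportive CMH rows, and the Cox treatment models, which contain no such interaction. This should be corrected because, followed literally, the rule gives misleading supportive results; it does not threaten the primary conclusion.

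**What to change.** Add one sentence to SAP 7.9.1: if the interaction p-value exceeds 0.10, the model is refitted with treatment arm and baseline MCL-1 dependence only, and treatment arm is tested in that refitted model. Alternatively, state that MCL-1 is centred at its pooled mean before fitting. Either restores power to 86-88% in the scenarios above.

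The same edit could say whether the rule applies to the combined CR and combined remission rates, and what is reported when the interaction p-value is 0.10 or less, on which the SAP is silent.

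The cost is a text change: same data, same software, and no effect on the primary analysis. It should be made before the Stage 2 comparison is seen, since choosing a refit or centring afterwards would be a post hoc repair. The SAP cites Amendment 7 and the protocol describes Amendment 11, so a SAP revision is due in any case.
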